#### 7.3.3 Medical History

General medical history data will be coded per MedDRA, summarized by system organ class (SOC) and preferred term (PT), and presented as a data listing (including CTCAE severity grade).

#### 7.5 Treatment and Medications

#### 7.5.1 Prior and Subsequent Anticancer Therapies

Prior and subsequent anticancer therapy is defined in Section 6.1.4. Number and percentage of subjects taking each prior and subsequent anticancer therapy will be summarized by type of therapy.

#### 7.5.2 Prior and Concomitant Medications

Prior and concomitant medications are defined in Section 6.1.3. Prior and concomitant medications will be coded by the World Health Organization (WHO) Drug Dictionary and summarized by Anatomic Therapeutic Chemical (ATC) Classification level 2 and PT.

#### 7.5.3 Exposure to Study Drug

Descriptive statistics will be used to summarize for acalabrutinib:

- Duration of exposure (months): (last dose date first dose date +1) / 30.4375
- Actual cumulative dose (g)
- Average daily dose (mg): (actual cumulative dose [mg]) / (duration of exposure [days])
- Relative dose intensity (RDI): (actual cumulative dose [mg]) / (duration of exposure [days] \*
   100 [mg] \* 2) \*100

Acalabrutinib dose withholding and reduction is based on the data from the dose administration CRF. The reasons for acalabrutinib dose withholding and reduction will be summarized.

- Dose withholding of acalabrutinib is defined as missing dose for ≥7 consecutive days.
- Dose reduction is defined as taking a lower dose level (100 mg per day) of acalabrutinib for ≥3 consecutive days.

Total exposure to rituximab will be summarized by descriptive statistics by each treatment time point, i.e. Day 1, 8, 15, and 22 of Cycle 1, and Day 1 of Cycles 2-6. For Part 3, subjects who have not progressed will received 10 additional doses of maintenance rituximab, every other cycle beginning with Cycle 8 (until Cycle 26, disease progression, or intolerance). Actual Dose administered is reported in mg. Rituximab dose reduction and interruption is based on the data from the dose administration CRF. The reasons for rituximab dose reduction and interruption will be summarized.

Descriptive statistics will be used to summarize for lenalidomide:

- Duration of exposure (months): (last dose date first dose date + 1) / 30.4375
- Actual cumulative dose (q)
- Average daily dose based on 21 days of 28 day cycle (mg): (actual cumulative dose [mg])
   / (number of planned lenalidomide dosing days [per CSP, first 21 days of each cycle]
   between subject's first and last dose of lenalidomide).
  - Number of planned lenalidomide dosing days can be calculated as: (duration of exposure [days]) - 7\*(number of cycles subject took any lenalidomide - 1 cycle).
  - Number of cycles subject took any lenalidomide can be calculated as: (duration of exposure [days]/28), rounded up to the nearest integer.

ACE-LY-003 Parts 2-3 Statistical Analysis Plan Version 1.0: 31Mar2022

- RDI: (average daily dose [mg]) / (assigned daily dose [15 or 20 mg])\*100 Lenalidomide dose withholding and reduction is based on the dose administration CRF. The reasons for lenalidomide dose withholding and reduction will be summarized.
  - Dose withholding of lenalidomide is defined as missing dose for ≥7 consecutive days (days 22-28 of each cycle are not considered as they are not dosing days).
  - Dose reduction is defined as taking lower than assigned dose level of lenalidomide for ≥3
    consecutive days (days 22-28 of each cycle are not considered as they are not dosing
    days).

Missing exposure data (e.g., the subject does not provide the dosing log for a certain time period) will be considered as dose of 0 mg for the calculation of summary statistics.

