MZL=marginal zone lymphoma; R/R=relapsed or refractory.

- Cohort 1 enrolling up to 40 subjects.
- ** Cohort 2 closed for further enrollment.

Samples for PD and molecular profiling will be collected according to sampling times in the Schedule of Assessments (Appendix 5). Tumor assessments will be performed at 12-week intervals in the first year and every 24 weeks thereafter during the study.

Refer to Appendix 5 for a comprehensive list of study assessments and their timing.

Part 3

This is a dose-finding, Phase 1b, multicenter, open-label study to be conducted at approximately 38 centers. Approximately 26 to 32 subjects with R/R FL will be enrolled and treated with acalabrutinib, rituximab, and lenalidomide (each cycle is 28 days). Once a safe and tolerable dose of lenalidomide has been established, 14 subjects (as part of the 26 to 32 subjects total) will be treated on the 3 drugs at that dose of lenalidomide.

- Acalabrutinib 100 mg PO BID administered approximately 12 hours apart (BID dosing=200 mg total daily dose), until disease progression or an unacceptable toxicity occurs.
- Rituximab 375 mg/m² IV administered on Days 1, 8, 15, and 22 of Cycle 1, and Day 1 of every cycle starting at Cycle 2 through Cycle 6, followed by 10 additional doses of maintenance rituximab every other cycle beginning with Cycle 8 for subjects who have not progressed.
- Lenalidomide will start at 15 mg PO QD for the first 6 subjects in Cycle 1.
 Doses up to 20 mg PO QD will be explored. Lenalidomide will be

administered on Days 1 through 21 of a 28-day cycle.

The study schematic for Part 3 is presented in Figure 2.

Figure 2 Study Schematic for Part 3

Cycle	1	2	3	4	5	6	8	10	12	14	16	18	20	22	24	26
Acalabrutinib 100 mg PO BID	Until progression or intolerance →															
Rituximab 375 mg/m² IV	Induction regimen Maintenance regimen															
	Xa	Х	X	X	X	X	X	X	X	Х	X	Х	X	X	X	X
Lenalidomide ^b PO D1-21/28d	Χ	Х	Х	X	Χ	X	Χ	Х	X							

BID=twice daily; D=day; DLT=dose-limiting toxicity; IV=intravenous; PO=by os (mouth); QD=once a day.

- a. Rituximab will be administered weekly on Day 1 during Cycle 1 and Day 1 of every cycle from Cycles 2 through 6. Subjects who have not progressed will receive maintenance rituximab every other cycle starting on Cycle 8 for 10 additional doses until disease progression or intolerance. Lenalidomide is to be taken daily on Days 1 through 21 of each cycle.

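### SAP 7.5.3 does not cap the last 28-day block at 21 planned lenalidomide days, so relative dose intensity is understated when the last dose falls on day 22 to 28 of a block

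*SAP*

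**What the plan says.** For lenalidomide, SAP 7.5.3 divides cumulative dose by the "number of planned lenalidomide dosing days [per CSP, first 21 days of each cycle"], restricted to the interval between the subject's first and last dose. It then supplies a computing rule: "Number of planned lenalidomide dosing days can be calculated as: (duration of exposure [days"], less 7 × (number of cycles − 1). The cycle count is itself derived from duration: "Number of cycles subject took any lenalidomide can be calculated as: (duration of exposure [days]/28), rounded up to the nearest integer". RDI is "average daily dose [mg]) / (assigned daily dose [15 or 20 mg"], times 100.

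The rules for withholding and reduction in the same section add that "days 22-28 of each cycle are not considered as they are not dosing days". The Figure 2 footnotes in Protocol 3.1 agree ("Lenalidomide is to be taken daily on Days 1 through 21 of each cycle") and allow up to 12 cycles.

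Both documents set a cycle at 28 days. Neither says whether, after a delay, a cycle is dated from its actual start or stays on a fixed 28-day grid from first dose.

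**The concern.** The computing rule subtracts a seven-day rest period for every 28-day block except the last. That is right if the last dose falls on or before day 21 of the last block. If it falls later, the last block contributes 22 to 28 planned days, although the section itself says those days are not dosing days. The denominator is then too large, and average daily dose and RDI too small.

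A small delay in a later cycle start is enough to cause this. At stake is how lenalidomide exposure is described in Part 3, whose primary objective is the safety of the three-drug combination. The protocol treats this kind of figure as informative: Sections 1.7 and 3.3 cite 64% lenalidomide dose intensity in the earlier study of ibrutinib with rituximab and lenalidomide.

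**Working it through.** **Inputs**
- D = days from first to last lenalidomide dose, inclusive (SAP 7.5.3).
- SAP formula: P = D − 7 × (ceil(D/28) − 1).
- SAP definition for n completed cycles: 21n planned days.
- s = net shift in days of the last cycle's start. The documents give no observed shifts, so s is an assumption. The Part 3 schedule (Protocol Appendix 6) shows a ±2-day visit window from Cycle 3 on, which makes s = 2 plausible from three cycles. Protocol 3.5.6 allows holds of up to 28 consecutive days but does not say that a hold moves the cycle start, so s = 7 is illustrative.
- All 21 doses of each cycle are taken at the assigned dose. RDI then equals 21n / P, and the definition gives 100%.

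**On schedule (s = 0).** D = 28n − 7. For twelve cycles D = 329 and P = 329 − 77 = 252 = 12 × 21. The formula is exact.

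**Late by 1 to 7 days, last cycle completed.** D = 28n − 7 + s, so ceil(D/28) = n and P = 28n − 7 + s − 7(n − 1) = 21n + s. The surplus is exactly s days, whether cycles are re-dated or kept on a fixed grid.

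| Cycles | Definition | s = 2 | s = 7 |
|---|---|---|---|
| 2 | 42 | not shown (see verdict) | D = 56; P = 56 − 7 = 49; 42/49 = 85.7% |
| 3 | 63 | D = 79; P = 79 − 14 = 65; 63/65 = 96.9% | D = 84; P = 84 − 14 = 70; 63/70 = 90.0% |
| 6 | 126 | D = 163; P = 163 − 35 = 128; 126/128 = 98.4% | D = 168; P = 168 − 35 = 133; 126/133 = 94.7% |
| 12 | 252 | D = 331; P = 331 − 77 = 254; 252/254 = 99.2% | D = 336; P = 336 − 77 = 259; 252/259 = 97.3% |

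**With the last block capped.** G = 21 × floor(D/28) + min(21, D mod 28). For D = 79, G = 42 + min(21, 23) = 63. For D = 331, G = 231 + min(21, 23) = 252. For D = 56, G = 42 + 0 = 42. Every entry in the table returns to 100%.

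**Last cycle not completed.** If the last dose is on day k < 21 of the last cycle, the surplus over the fixed grid is max(0, k + s − 21). With six cycles and s = 4:
- k = 18: D = 162, P = 127, G = 126, a surplus of 1.
- k = 14: D = 158, P = 123, G = 123, no surplus.

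If cycles are re-dated, the surplus is s = 4 in both cases.

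**Outside the 1-to-7-day range (two cycles, 42 doses).** Here the formula and the capped count agree:
- 2 days early: D = 47; P = G = 40; 42/40 = 105.0%.
- 8 days late: D = 57; P = G = 43; 42/43 = 97.7%.
- 14 days late: D = 63; P = G = 49; 42/49 = 85.7%.

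**The case against.** The SAP's wording is permissive (the days can be calculated this way), and the correct definition stands beside the formula. The formula is exact on schedule, and missed doses within an unshifted cycle do not disturb it. If held doses are skipped and later cycle starts stay put, D does not change and the error does not arise. At twelve cycles even a 7-day shift costs only 2.7 points, and no efficacy analysis or dose decision uses RDI.

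All of this stands, and it limits the size of the point. It does not remove it: the formula is the only algorithm given, so it is the one likely to be programmed, and for a completed last cycle 1 to 7 days late it contradicts the definition on either reading of a cycle.

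A reader might go further and infer that RDI is wrong for every subject whose cycle starts shift, citing the 105.0% for an early start or the values at 8 and 14 days late. The documents do not support that. Those values depart from the definition only if cycles are re-dated, which the SAP does not say; on a fixed grid the formula is right there. The jump from 85.7% at 7 days to 97.7% at 8 days comes from the missing cap at 7 days: the capped count gives 100% and then 97.7%.

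**Conclusion.** The point holds for a last dose on day 22 to 28 of a block counted from first dose. The denominator is then 1 to 7 days too large. With all doses taken and the last cycle completed, the shortfall in RDI at a 2-day delay is 3.1 points at three cycles, 1.6 at six and 0.8 at twelve. At an assumed 7-day delay it is 14.3 points at two cycles, 10.0 at three, 5.3 at six and 2.7 at twelve. These figures do not describe a subject who restarts at a reduced dose. How many of the planned 26 to 32 Part 3 subjects would be affected is unknown. This is a minor correction to a descriptive summary.

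Two further inferences should not be drawn. First, a reader might apply the ±2-day window to Cycle 2 and quote a two-cycle, in-window error. In the schedule text available the Cycle 2 window cell is blank, and Protocol Appendix 12 lists a ±2-day Cycle 2 header as a Canada-specific change. Even from Cycle 3 the window governs visits; that lenalidomide Day 1 moves with the visit is an assumption. Second, a reader might measure the formula against the acalabrutinib rule, "Average daily dose (mg): (actual cumulative dose [mg]) / (duration of exposure [days"], which counts every calendar day. The SAP sets no such benchmark for lenalidomide.

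**What to change.** Replace the planned-days formula in SAP 7.5.3 with 21 × floor(D/28) + min(21, D mod 28), and add a sentence that it uses a fixed 28-day grid from first dose. The cost is one formula, one sentence and the matching program line.

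The cap leaves early starts and shifts above 7 days at the SAP's present values, including the two-cycle 105.0%, 97.7% and 85.7% shown above. If the sponsor means re-dated cycles, it should say so and count days 1 to 21 from each recorded cycle start, up to the last dose. That needs cycle start dates. The section names a source only for withholding and reduction ("Lenalidomide dose withholding and reduction is based on the dose administration CRF") and does not say whether cycle starts are captured, so the cost of this option cannot be judged from the documents. RDI counted this way would not reflect delays between cycles, and the SAP should say that too.

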3.5.4 Assuring Subject Compliance

Subjects will receive their supply of acalabrutinib in the clinic on Day 1 of Cycle 1 and Cycle 2, and Day 1 of subsequent scheduled visits. For treatments that are taken in the clinic, subjects should take acalabrutinib from the drug dispensed for them for that particular time period. All other acalabrutinib treatments will be taken at home. Subjects will receive a diary to record the specific time each dose was taken and to record reasons for any missed doses.

Subject compliance will be assessed at every visit. The subject will be instructed to bring the diary and any remaining capsules or tablets to the clinic at their next visit. The administrator will review the diary and ask the subject if all the capsules or tablets were administered. Any remaining or returned capsules and tablets will be counted and recorded as described in Section 7.11. Returned capsules and tablets must not be redispensed to another subject. The study staff will resupply the subject with the correct number of capsules or tablets needed for use until the next visit.

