5.4 MISSING DATA HANDLING

General Considerations: Subjects lost to follow-up (or who dropped out) will be included in statistical analyses up to the point of their last evaluation.

Duration of Response and Progression-Free Survival: Data for subjects without disease progression or death will be censored at the date of the last tumor assessment and before the initiation of alternative anticancer therapy. The details of the censoring rules will be provided in the Statistical Analysis Plan (SAP).

Time-to-Next Treatment: Data from subjects who have not received subsequent therapy will be censored at the earliest of death or the last time that lack of administration of a new therapy was objectively documented. The details of the censoring rules will be provided in the SAP.

Safety: Missing or partial start and end dates for AEs and concomitant medications will be imputed according to prespecified, conservative imputation rules. The details will be provided in the SAP. No other imputation of values for missing data will be performed.

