5.5.3 Study Treatment Administration and Compliance

Descriptive information will be provided regarding the number of acalabrutinib, lenalidomide, and rituximab doses prescribed, the total number of doses taken, the number of days of treatment, and the number and timing of prescribed dose reductions and interruptions.

For each subject, acalabrutinib and lenalidomide compliance will be described in terms of the proportion of study drug actually taken based on returned pill count relative to the amount that was dispensed (taking into account physician-prescribed modifications and interruptions).

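### SAP 7.5.3 scores periods without a dosing log as 0 mg but keeps them in the denominator, so relative dose intensity and average daily dose can only be biased low

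*SAP*

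**What the plan says.** SAP 7.5.3 closes with a rule for missing exposure data. Its own example is that "the subject does not provide the dosing log for a certain time period", and such data "will be considered as dose of 0 mg for the calculation of summary statistics". The rule stands at the end of the section and is not limited to one drug.

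For acalabrutinib, the section divides cumulative dose by the days from first to last dose times 200 mg. For lenalidomide, it divides cumulative dose by the planned dosing days between first and last dose, and then by the assigned daily dose. Neither denominator removes days without a log.

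SAP 6.2 sets the general convention: apart from partial dates, missing data are left missing. SAP Section 8 lists two changes from the protocol, the efficacy-evaluable definition and the time-to-event reference date. The 0 mg rule is not among them.

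Protocol 5.5.3 describes compliance for acalabrutinib and lenalidomide as the "proportion of study drug actually taken based on returned pill count relative to the amount that was dispensed". Protocol 3.5.4 adds that "Any remaining or returned capsules and tablets will be counted and recorded as described in Section 7.11". The SAP makes no use of pill counts.

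**The concern.** A log that was not returned shows that the dose is unknown. It does not show that the dose was not taken. The rule turns an unknown into a known zero, and because the days stay in the denominator the error has only one direction.

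Safety is the primary objective of Part 3, which is a dose-finding part. A reader of the exposure tables will use lenalidomide RDI and average daily dose to judge how much of the assigned dose was delivered. Under the rule, a paperwork loss lowers those figures exactly as a real interruption would, and the tables give no means of telling the two apart. The planned pill count could fill some of these gaps, but the SAP does not use it.

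**Working it through.** The documents state no RDI and no missing-log rate, so there is no figure to reproduce. The check applies the SAP 7.5.3 formulas to a subject who took every dose but has unlogged days inside the exposure span.

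**Inputs**
- Acalabrutinib: 200 mg per day; D = days from first to last dose; m = unlogged days (SAP 7.5.3).
- Lenalidomide: planned days P = D − 7 × (cycles − 1), with cycles = D/28 rounded up (SAP 7.5.3).
- Length of one log: 28 days from Cycle 3 to Cycle 12, when visits are on Day 1 only (Protocol Appendices 5 and 6). In Part 2 it is 84 days after Cycle 13, when clinic visits are every 3 cycles (Appendix 5).
- Long exposure span: 913 days, about 30 months × 30.4375. The 30 months is borrowed from the median follow-up in Protocol 3.2; using it as exposure time is an assumption.

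**Acalabrutinib**, RDI = (D − m) × 200 / (D × 200)
- 12 cycles, one 28-day log lost: 308/336 = 91.7%; average daily dose 0.917 × 200 = 183.3 mg.
- 913 days, one 84-day log lost: 829/913 = 90.8%.

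**Lenalidomide**, RDI = (P − m)/P, where one 28-day log holds 21 dosing days
- 12 cycles: D = 11 × 28 + 21 = 329; P = 329 − 7 × 11 = 252; 231/252 = 91.7%. Average daily dose is 13.75 mg for an assigned 15 mg, or 18.33 mg for an assigned 20 mg.
- 6 cycles: D = 5 × 28 + 21 = 161; P = 161 − 7 × 5 = 126; 105/126 = 83.3%.

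**Effect on a group mean.** If a share s of fully adherent subjects loses one period, mean acalabrutinib RDI falls by s × m/D. The range for s is assumed.

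| s | 28 of 336 days | 84 of 913 days |
|---|---|---|
| 5% | 0.4 points | 0.5 points |
| 10% | 0.8 | 0.9 |
| 20% | 1.7 | 1.8 |
| 30% | 2.5 | 2.8 |

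Small groups are more exposed. In a six-subject lenalidomide dose group, one such subject lowers the mean RDI by 8.3/6 = 1.4 points over 12 cycles, or 16.7/6 = 2.8 points over 6.

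**When the bias is zero.** It vanishes if the unlogged doses really were not taken, or if the gap is at the end and the last dose date comes from the log, so that the gap drops out of the span. Removing the unlogged days from both sides returns the fully adherent subject to 100% in every case above.

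**The case against.** The sponsor can fairly say that this is a disclosed, prespecified convention for a descriptive summary. SAP Section 6 allows missing data to be imputed where specified, SAP 6.2 speaks only of the general case, and 7.5.3 specifies an exception. No planned analysis relates response or toxicity to RDI, and lenalidomide dose decisions rest on dose-limiting toxicity counts. The effect on the mean is probably small. All of that stands. It does not remove the one-directional error or supply a reason for the exception.

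Pill counts are also imperfect. Dispensed minus returned treats unreturned drug as taken, and Protocol Appendix 9 foresees subjects who fail to return it. Diary and leftover drug are due at the same visit, so both can be lost. The diary and accountability text in Protocol 3.5.4 and 7.11 is written around acalabrutinib; for lenalidomide the pill count rests on 5.5.3. This limits the fix but does not defeat it.

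Four stronger readings are tempting and are not supported:

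- **A direct conflict with Protocol 5.4.** The sentence "No other imputation of values for missing data will be performed" closes the paragraph on safety, which deals with adverse event and concomitant medication dates. It need not reach exposure.
- **Lost diaries will be reported as withholding.** The SAP says "Dose withholding of acalabrutinib is defined as missing dose for ≥7 consecutive days", and a 28-day gap is four times that length. But withholding is taken from the dose administration CRF with reasons, and the 0 mg rule is confined to summary statistics. The misclassification is possible, not stated.
- **One lost log takes a 3-cycle lenalidomide subject to 42/63 = 66.7%.** Appendix 6 checks compliance weekly in Cycle 1 and mid-cycle in Cycle 2. One lost log there covers at most 7 or 14 dosing days, giving 56/63 = 88.9% or 49/63 = 77.8%.
- **The rule reproduces the 64% lenalidomide dose intensity cited in Protocol 1.7 and 3.3.** That is a study-level figure for the ibrutinib triplet and cannot be set against one hypothetical subject.

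**Conclusion.** The point holds as a bias in descriptive exposure summaries. By construction, the 0 mg rule can lower RDI and average daily dose and can never raise them. For a fully adherent subject with one lost 28-day log after Cycle 2, the loss is 8.3 points over 12 cycles for either drug and 16.7 points over 6 cycles for lenalidomide. These figures assume that every dose was taken, that the gap is followed by logged dosing, and that lenalidomide is logged over the same periods as acalabrutinib. The overall size is unknown because the missing-log rate is not given; the 0.4 to 2.8 point range depends on the assumed 5% to 30%.

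The overall response rate and the dose-limiting toxicity decisions do not depend on this rule. The change is worth making because it corrects a known direction of error at little cost.

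**What to change.** Replace the closing sentence of SAP 7.5.3 with a rule along these lines:

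1. For a period without a log, derive the dose from the returned pill count in Protocol 5.5.3 where it is available, and state that unreturned drug then counts as taken.
2. Where no count is available, remove the period from both numerator and denominator. This assumes that intake in the gap was like intake in the logged periods, and the SAP should say so.
3. Report, by drug and treatment group, the number of subjects and days affected and how each gap was filled.
4. Keep the 0 mg version as a worst-case sensitivity analysis. With the pill-count version, it shows how far the result depends on the missing logs.
5. State that a gap without a log is not by itself counted as withholding unless the dose administration CRF records a withheld dose.
6. List the rule in SAP Section 8.

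The cost is SAP wording, minor programming and a pill-count reconciliation for each affected period. It needs no data beyond what the protocol already plans to collect.
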